5.4.2 Exclusion Criteria

- 231 Exclusion criteria are systemic infection, immunosuppressive disorder, implanted electronic devices,
- pregnancy, previous allergy to skin contact materials and/or anesthetic agent altered mental status, inability
- 233 to provide consent, greater than 180 morphine equivalents (MED) per day.

234 5.5 Study Plan

- The study includes 13 Visits. Please refer to the Appendix for a schedule of study procedures for both
- 236 groups as well as outcomes measured at each visit.
- Patients planned for nontraumatic TFA or TTA will be screened by the study investigators who are working
- on the Acute Pain Service (APS). APS is usually consulted for all transferoral and transtibial amputations
- 239 to provide perioperative anesthesia, which typically includes placement of a peripheral nerve catheter for
- local anesthetic blockade. When a potential subject is identified, study investigators will begin a chart
- review for screening purposes. The investigators will review the medical record of potential subjects and
- complete Form 00 (Screening and Demographic Information). Chart review will include the collection of
- name, social security number and date of birth from CPRS, the ORC, and the Vascular Clinic. Protected
- Health Information (PHI) will be used to locate and review appropriate medical records (CPRS and paper
- medical records) to determine study eligibility. If a subject appears to meet all eligibility criteria (see
- 245 incident records) to determine study engionity. If a subject appears to ineet an engionity enterta (see
- Section 5.4. Eligibility), then he/she will be contacted by study investigators and given recruitment
- 247 materials detailing study objectives, randomization, procedures, follow-up encounters, assessments, and
- 248 potential risks and benefits. The subject will be provided with patient information pertaining to the
- 249 peripheral nerve stimulator system under investigation. If permitted by the subject, a sponsor representative
- or their designee may be present at any of the study visits to advise on material handling and answer
- questions as needed.

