- The duration of this investigation is expected to be 18-24 months. We anticipate enrolling 2-4 patients per 454
- month. Each patient's participation will last approximately 12 months. 455

Data Management 6.0

Sample Size

- The investigation seeks to broaden the knowledge of the effects of neuromodulation on acute post-operative 458
- pain in nontraumatic lower extremity amputation. The aim is to evaluate the feasibility of implementing 459
- PNS in TFA or TTA in the acute post-operative period. 16 subjects will be randomized into two groups 460
- 461 with 8 each. Sampling will not be restricted by race or gender. The sample size of 16 is expected to allow
- the investigators to conduct a cost-effective yet informative pilot study to assess the logistics of placing the 462
- 463 device as described in this protocol, evaluate safety, and report any clinically significant differences in
- primary and secondary outcomes between Treatment and Control Groups. The study outcomes will be 464
- 465 reported in nontraumatic TFA or TTA, many of which are secondary to dysvascular disease. Although this is a specific subset of all amputations that are performed, dysvascular disease accounts for a sizeable 466
- proportion of limb loss in the US with an estimated prevalence of 38-82% (24, 25). The results of this 467
- investigation will be used to refine the study design, recruitment, randomization, retention, and assessment 468
- 469
 - procedures, and ultimately develop a larger, multicenter, randomized controlled trial to further evaluate

470 treatment efficacy, adverse effects, and cost efficiency. To improve generalizability, subsequent

471 investigations will seek to include a wider subset of amputations which may be accomplished with the

472 addition of more study sites.

473

490

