6.2 Sampling and Randomization Procedures

Based upon historical data on amputations at the HHM-VAMC, there are estimated to be one to two 474 475 amputations per week that would qualify for enrollment in this study. Subjects will be screened for enrollment through the vascular surgery clinic. A considerable proportion of vascular clinic patients will 476

require lower extremity amputation and are usually scheduled for next day surgery due to the urgency of 477

presentation. Study investigators will conduct a chart review of potential subjects and complete Form 01-478

479 A (screening and demographic information). Based on the chart review, if a patient appears to meet all 480

eligibility criteria, then they will be contacted by study investigators for potential enrollment. If the patient

agrees to participate, they will be consented and randomized to Group 1 or Group 2. 481

482 Prior to the start of this study, a member of the study staff that is not involved with recruitment or data

483 evaluation will be responsible for generating a random string of group assignments long enough to fill all

anticipated spots in this study. The numbers will be placed in secure envelopes by blocks of two. A block 484

485 of two will contain one assignment to the Treatment Group and one assignment to the Control Group. As

486 subjects are consented and enrolled in the study, they will be assigned an envelope which randomizes them

487 to a group. Subjects are not blinded to their group assignments. Subjects in the Treatment Group will

receive the investigational treatment (30 to 60-days of peripheral nerve stimulation) in addition to SMT. 488

489 Subjects in the Control Group will be treated with the SMT alone.

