6.3 Data Analysis

A table of outcome measures recorded during the study can be found in Appendix. Scores rating daily 491 492 average, worst, and least pain will be compared between groups. Changes in pain will be evaluated for

individual subjects and compared between groups. For each subject, mean pain scores over the first and 493

494 second months following TFA or TTA surgery will be calculated. An overall mean across all subjects will

be calculated. Additionally, sub-analyses will be performed to determine if there is a difference in these 495

outcomes between groups over different post-operative phases (such as acute (e.g. days 1-30) or subacute 496

497 (e.g., 1-3 months), or chronic (e.g. >3 months)). Statistical analysis will be performed with two-sample t-

498 test, and p-values will be reported without adjustment, consistent with feasibility study design and the

499 number of subjects.

500 Pain medication usage will be recorded in subject diaries and obtained during follow up encounters. Opioid

medication use will be analyzed by averaging 24-hour morphine equivalent dosing (MED) over each 501

502 follow-up interval and comparing groups. Changes in opioid medication use will be reported for individual

503 subjects by calculating morphine equivalent dosing (MED). Average MED will be calculated and compared between groups. The time to cessation of opioid use will be reported. Side effects associated 504

with opioid use will be assessed at each visit and the number of side effects occurring over various intervals 505

506 will be recorded. Analgesic-related outcomes will be compared between the Groups.

507 Patient Global Impression of Change (PGIC), Pain Catastrophizing Scale (PCS), and Pain Disability Index

508 (PDI) scores will be averaged for each group and compared. Data regarding functional outcomes

509 (Functional Independence Measure [FIM] score), time to wound healing, incidence of neuromas, prosthesis

fitting, time to hospital discharge, 30-day readmission rate, and hospital discharge survey will be compared 510

between groups. 511

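### Average MED is compared between groups of 8 with no account of pre-admission opioid use, so chance imbalance in long-term users can make the opioid estimate imprecise or wrong in direction

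*Combined protocol and SAP*

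**What the plan says.** - **Entry.** Section 5.4.2 sets the only opioid limit, excluding subjects on "greater than 180 morphine equivalents (MED) per day". Intake from 0 to 180 MED/day is therefore admissible. The section does not say at what time the limit is assessed.
- **Size and allocation.** Section 6.0 (Sample Size) states that "16 subjects will be randomized into two groups" of 8. Section 6.2 randomizes in blocks of two, where each block "of two will contain one assignment to the Treatment Group and one assignment to the Control Group". Allocation is not stratified by prior opioid use.
- **Opioid analysis.** Section 6.3 says that opioid "medication use will be analyzed by averaging 24-hour morphine equivalent dosing (MED) over each" follow-up interval, with groups then compared. It adds: "Changes in opioid medication use will be reported for individual" subjects, without naming a reference value. It continues: "Average MED will be calculated and compared between groups. The time to cessation of opioid use will be reported". The paragraph closes with: "Analgesic-related outcomes will be compared between the Groups". The only test named in Section 6.3 is the two-sample t-test.
- **Medication records.** The Appendix schedule places the first pain-medication entry at Visit 1. Section 5.5.1 puts that visit at least 24 to 48 hours after the nerve block catheter is removed. Section 4.2.5 provides for a query of the state prescription-monitoring database but states no look-back before admission.

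No section uses pre-admission opioid intake as a covariate, stratum, subgroup or reference value.

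**The concern.** Whether PNS lessens opioid use is one of the study questions in Section 1.2, and Section 6.0 expects the sample to show clinically significant differences in secondary outcomes. A subject who took opioids long term before admission may go on taking them whatever happens to the amputation pain. With 8 per group, the arm such a subject falls into can weigh as much in the MED difference as the treatment does.

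The plan has no tool to separate the two. Visit 1 reflects acute postoperative dosing, so even a change from Visit 1 would not recover background intake. Time to cessation has a related gap: for a prior user it mixes recovery from surgery with an older habit of use, and no rule covers a subject who never stops. At stake is a pilot estimate of opioid sparing that would inform the larger trial.

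**Working it through.** **Inputs from the documents.** 8 subjects per group (Section 6.0); admissible intake 0 to 180 MED/day (Section 5.4.2); blocks of two (Section 6.2); two-sample t-test (Section 6.3).

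**Not in the documents, so assumed.** The number of long-term users, their dose, how far it persists, the SD of follow-up MED, the PNS effect, and a two-sided 0.05 level.

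The plan gives no effect size, SD or power for MED, so there is no figure of its own to reproduce. For context, 8 per group at two-sided 0.05 and 80% power detects a standardised difference of 1.40 (normal approximation) or 1.51 (noncentral t).

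**Step 1: shift in a group mean.** Shift = extra MED / 8.
- 60/8 = 7.5; 90/8 = 11.25; 120/8 = 15; 180/8 = 22.5 MED/day.
- Two subjects at 180 in one arm: 360/8 = 45.
- The 22.5 is a ceiling for one subject: the highest admissible dose, persisting in full, against zero.

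**Step 2: chance of imbalance.**
- One long-term user: the arms are always unequal.
- Two users under blocks of two: same arm with probability 14/15 × 1/2 = 46.7%.
- Four users among 16: P(2-2) = 28 × 28/1820 = 0.431; P(3-1) = 2 × 56 × 8/1820 = 0.492; P(4-0) = 2 × 70/1820 = 0.077. An unequal split has probability 0.569.
- If 10%, 20% or 30% of subjects are long-term users, a simulation of two arms of 8 gives a difference of at least one user in 64.5%, 75.0% or 78.4% of trials, and of at least two in 19.2%, 33.9% or 41.1%.

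**Step 3: what the planned t-test makes of it, with no treatment effect.** Take four users at 100 MED/day and all others at 0.
- 3-1 split: means 37.5 and 12.5, difference 25. Variances 18,750/7 = 2,678.6 and 8,750/7 = 1,250. SE = √((2,678.6 + 1,250)/8) = 22.2; t = 1.13 on 14 df; p = 0.28.
- 4-0 split: difference 50. Variance 20,000/7 = 2,857.1 in one arm and 0 in the other. SE = √(2,857.1/8) = 18.9; t = 2.65; p = 0.02.

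The users widen the SD as well as moving the mean, so a difference of 25 MED/day is visible but not significant.

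**Step 4: precision and direction when PNS works.** Simulation, 4,000 runs per case. Assumed: other subjects' follow-up MED has mean 40 and SD 20, the true effect is -20 MED/day, and background intake persists in full.

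| Long-term users | Extra MED/day | Power, t-test | Wrong sign, t-test | Power, adjusted | Wrong sign, adjusted |
|---|---|---|---|---|---|
| 0 | 0 | 46% | 2% | not applicable | not applicable |
| 1 | 60 | 32% | 6% | 44% | 2% |
| 1 | 120 | 18% | 18% | 42% | 3% |
| 1 | 180 | 8% | 33% | 43% | 3% |
| 2 | 60 | 23% | 9% | 43% | 3% |
| 2 | 120 | 14% | 22% | 42% | 3% |
| 2 | 180 | 9% | 25% | 43% | 3% |

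With one or two users, the SD of the estimated difference is 12 to 32 MED/day unadjusted and about 10 adjusted. With no true effect, the unadjusted t-test rejected in 0.2% to 4.8% of runs in these cases. Full persistence is the case most favourable to adjustment; weaker persistence would reduce both the problem and the gain.

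**Step 5: time to cessation.** One subject who never stops is 1/8 = 12.5% of an arm, and that subject has no observed cessation time to report.

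**The case against.** Several counter-arguments have force.

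- **No false result follows.** A reader might infer that one or two long-term users bias the comparison or produce a spurious significant finding. The documents and the arithmetic do not support that. Allocation is randomized, so the imbalance is chance, and Steps 3 and 4 show the t-test usually staying non-significant. This stands.
- **Low weight.** MED is a secondary outcome in a 16-subject pilot with no power calculation, and Section 6.3 presents its p-values as suited to a feasibility design. On the assumptions above, power is only 46% even with no long-term users. This stands and limits the severity.
- **Change may already be compared.** A reader might take Section 6.3 to limit change in opioid use to individual reporting. The closing sentence on analgesic outcomes can be read to bring change into the group comparison, just as it brings in time to cessation. That is a fair reading, but the reference for change is still undefined and the first scheduled record is still postoperative.
- **Pre-admission MED may not be on hand.** It is tempting to say the eligibility limit requires it already. Section 5.4.2 gives no time point, and Section 5.5 allows enrollment after surgery, so the limit could be applied to in-hospital intake. A pre-admission average may be new data. Equally, Form 00, which Section 8.2 says covers the eligibility criteria, is not among the documents and may capture part of it.
- **Redefining cessation.** Treating return to pre-admission MED as cessation is debatable. The earlier opioids may have been taken for the limb later amputated, so unchanged intake would count as success. This stands, and it rules out that definition as a replacement.
- **Adjustment is not magic.** With a single long-term user, adjusting for pre-admission MED amounts to removing that subject from the comparison. This is true, and it is a reason to show individual data beside the adjusted estimate.

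**Conclusion.** The point holds as a gap in precision and interpretation. Section 6.3 compares raw interval MED between groups of 8 although prior intake may range from 0 to 180 MED/day, and nothing in the analysis uses that intake. The upper bound of 22.5 MED/day for one subject rests only on the group size and the entry limit, with full persistence against a zero comparator. The losses of power and the wrong-sign rates rest on the assumed mean, SD, effect and persistence, and show scale only. The documents do not say how many long-term users to expect, or that prior use is the main determinant of later MED. They support no claim of bias or of frequent false significance. The change is worth making because it is cheap and the pilot feeds a larger trial, but its weight is modest.

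**What to change.** 1. Record pre-admission MED for every subject, with a stated look-back period, from the screening chart review and the prescription-monitoring query. Tabulate it by group.
2. In Section 6.3, compare interval MED between groups adjusted for pre-admission MED, or compare change from it. Name this value as the reference for change in opioid use.
3. Show individual data beside the group estimate, and list prior users and non-users separately.
4. Report time to opioid cessation separately for subjects with and without pre-admission use, and treat those who never stop as censored at last follow-up. Return to at or below pre-admission MED may be added as a supplementary description, not as a replacement definition.

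The cost is one data field, one degree of freedom out of 14, and a few sentences in Section 6.3. The eligibility limit and clinical care do not change.

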7.0 Risks and Benefits

7.1 Potential Benefits

It is possible that subjects in this study may not receive any direct benefit from their participation in this study. If the investigational treatment is successful, subjects in the Treatment Group may have a reduction in acute post-amputation pain, decreased probability of developing chronic post-amputation pain, less interference due to pain, decreased opioid medication use, increased tolerance for rehabilitation and accelerated functional improvement. This research may benefit future patients with post-operative pain following TFA or TTA.

7.2 Potential Risks

The devices used in this study have been cleared by the United States Food and Drug Administration to provide postoperative analgesia. Potential risks include infection, lead fracture, lead migration and/or dislodgement, nerve injury, bleeding, skin irritation, increased pain, and discomfort on insertion, during use or with withdrawal. However, there may be other risks that are currently unknown. The incidences provided are all estimated except for lead fracture. The risks listed below are described as either common (occurring more than 10% of the time), uncommon (occurring about 2-10% of the time), or rare (occurring less than 1% of the time).

7.2.1 Infection

Based on previous studies using this PNS system, the risk of infection is rare. When compared to continuous femoral nerve block and/or continuous sciatic nerve blocks, the risk of infection from a percutaneously placed lead near these nerves is expected to be lower. The risk is thought to be mitigated by the inherent structure and design of the lead. Unlike nerve block catheters, PNS leads do not have an internal conduit through which bacteria can enter the body. The coiled structure of the fine wire lead allows it to stretch when pulled, rather than move into or out of the insertion site. This is thought to minimize the potential of introducing bacteria into the body. Lastly, the electrode is designed to have a tight electrodeskin barrier to help prevent bacterial inoculation. Infection risk will be minimized by using sterile leads and thoroughly cleansing the insertion site with antibacterial solution at the time of insertion. The insertion site will be covered with a dressing to keep it clean and dry, and the subjects will be instructed to inspect the site for signs of infection or irritation regularly and to inform the investigator if they occur. If infection occurs, the investigator may administer an antibiotic and/or remove the lead.

7.2.2 Lead fracture

Lead fracturing beneath the skin is a common risk, with most or all fractures occurring during the procedure to remove the lead. When this occurs, one or more lead fragments may remain in the body. Granuloma (mild tissue inflammation) is directly related to the risk of retained electrode fragments. The investigators will inspect the lead after removal to determine if any fragments were retained in the body. If there is suspicion of a retained fragment, the investigator will determine if removal of the lead is medically necessary. In most cases, removal is not necessary unless there are further sequalae associated with the fragment, such as infection or granuloma. Retained fragments may also be removed if the subject desires. The impact of retained fragments *in situ* is minimal and in most cases, retained fragments do not need to be removed.

7.2.3 Lead migration and/or dislodgement

It is possible for a lead to migrate from its original position or become dislodged (i.e. entirely removed from the insertion site) during the 30-day treatment period. This is a common risk. If migration occurs, the subject may experience discomfort during stimulation. Stimulation near the skin surface may be perceived

as "pins and needles" which may be uncomfortable to the subject. Please see below for the steps taken cases of discomfort associated with the PNS system. In cases of significant migration or complete dislodgement, a replacement lead may be inserted depending on the desires of the patient and time remaining in the treatment period.

The risk of lead migration or dislodgement is reduced by providing instructions to the subject and their caregiver, as appropriate, to ensure careful handling of the lead and lead connector during bandage changes. Discomfort or pain due to stimulation may occur if the lead migrates from its original location. Stimulation near the skin surface may be perceived as a "pins and needles" sensation and may be uncomfortable. Stimulation parameters or a new lead may be placed if necessary for additional comfort. A tingling sensation may be felt under the pad but this sensation is not expected to be uncomfortable.

7.2.4 Nerve injury

 The risk of mechanically damaging a nerve with the introducer is rare and will be mitigated by using ultrasound to visualize the nerves, surrounding landmarks, and relative position of the introducer. Though the lead placement procedure is like the procedure used for regional anesthesia nerve blocks, the lead can be placed further away from the nerve when compared to placement of nerve block catheters. The risk of nerve injury may be further reduced by proper subject positioning and slow advancement of the introducer, stopping approximately 0.5 - 3 cm proximal to the nerve.

7.2.5 Bleeding

The risk of bleeding from lead placement is rare and is expected to be no greater than the risk of bleeding related to peripheral nerve block catheters. INR for anticoagulated patients will be available for review as patients undergoing surgery will have this checked as a part of routine pre-operative assessment.

7.2.6 Skin irritation

It is a common risk for skin to become irritated at the lead exit site, under the stimulator pad (a modified surface electrode that is positioned between the skin and the stimulator device), in the area surrounding the lead insertion site, and at the site where an adhesive bandage and lead connecter are taped to the skin. Skin irritation is reduced by excluding patients with known sensitivity to skin-contact materials (stickers, bandages, tape etc.). Subjects and their caregivers will be advised to examine the electrode exit site at regular intervals to look for any signs of irritation. To avoid irritation under the pad and lead connector tape, subjects will be advised that the stimulator and pad may be moved to various locations near the lead insertion site throughout the study. To avoid irritation under the belt, subjects will be instructed to move the belt as needed. In addition, subjects will be instructed to avoid placing the pad, belt, lead connector tapes, or bandages on unhealthy skin.

